To evaluate cognitive performance changes (A3), we will compare cognitive performance change from pre-intervention to post-intervention) between active tDCS and sham groups. We hypothesize that the active tDCS group will have a larger improvement in cognitive performance than the sham group.

To evaluate substance use status during participation and 1- and 2-months later (A4), we will administer the Timeline Follow Back(Sobell and Sobell 1996) questionnaire, assess the number of days of opioid use, and amount at peak use at follow-up (1- and 2-months later). We will also collect saliva/urine samples as often as every week. Based on our alcohol pilot study and literature on the effect of tDCS in other addictions (Lupi et al. 2017; Batista et al. 2015), we hypothesize that the active tDCS group will have lower followup substance use rates and longer abstinence periods than the sham group.

3.2 Secondary Endpoint(s)/Event(s)/Outcome(s): To determine generalization and durability of cognitive training, patients will be asked to complete the following tasks at pre-intervention, post-intervention, 1-month follow-up and 2-

PROTOCOL TITLE: Combining Neuro-Imaging and Non-Invasive Brain Stimulation for Clinical Intervention in Opioid Use Disorder

VERSION DATE: 2022-02-11

month follow-up to examine generalization and durability effects of training: D-KEFS Trail Making Test, D-KEFS Verbal Fluency, D-KEFS Color Word, Digit-Span (WAIS-WISC), Digit Symbol (WAIS-WISC).

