4.2 Biosafety: N/A

4.3 Stem Cells: N/A

5.0 Procedures Involved

5.1 Study Design:

This study is double-blind, within subject, within study staff, and sham-controlled. The scientific integrity of the trial and the credibility of the data from the trial depend substantially on the trial design. A description of the trial design includes: In a double-blind randomized design, up to 250 individuals with a

PROTOCOL TITLE: Combining Neuro-Imaging and Non-Invasive Brain Stimulation for Clinical Intervention in Opioid Use Disorder

VERSION DATE: 2022-02-11

current opioid use disorder (OUD) diagnosis, age 18-60 years, enrolled in a methadone or buprenorphine treatment program and clinically stable will be recruited. Patients will receive 10 days (1 20-minute administration per day) of either (i) transcranial direct current stimulation (tDCS) to PFC or (ii) sham-tDCS. All subjects will perform cognitive training during tDCS intervention (active or sham) to prime the engagement of the NAcc-PFC brain circuit. Rest fMRI will be collected pre-intervention, at the midpoint of intervention, and post-intervention. The purpose for adding the midpoint MRI is to increase the statistical power of showing the trend of the experimental treatment's effectiveness over time. Follow-up interviews will be conducted 1- and 2-months after intervention completion to query substance use.

To examine generalization and durability effects of training, patients will be asked to complete the following tasks at pre-intervention, post-intervention, 1-month follow-up and 2-month follow-up: D-KEFS Trail Making Test, D-KEFS Verbal Fluency, D-KEFS Color Word, Digit-Span (WAIS-WISC), Intra-Extra Dimensional Set-Shift Task. Saliva/Urine tests checking for substance use will be administered at each follow-up timepoint.

5.2 Study Procedures:

Randomization: Random permuted blocks (subgroups of 4) will be used to ensure equal group assignment (active or sham tDCS) at predefined equally spaced points in the sequence of patient assignment. Blinding: Participants will not be informed on their assigned protocol. During consent, they will be informed that there is a 50% chance of receiving active tDCS or sham tDCS every visit for five study visits.

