VISITS 11-15: Will involve cognitive training tasks concurrently with tDCS, with tDCS for the first 20 minutes (46 minutes total per day). We will first remind the participant what the tasks entail and detail tDCS procedures. TDCS side-effects questionnaire will be administered daily before and after intervention.

During tDCS intervention (active or sham) the participant will be seated in a reclining chair while the participant perform the reversal learning task. Total participation time for days 3-7 will be about 1 hour each day, or about 5 hours over a period of 2 weeks.

VISITS 16-17/POST-INTERVENTION: At the post-intervention assessments and MRI, the participant will be administered the same clinical assessments, cognitive assessments, and substance use questionnaires as Visits 9-10. Craving will be re-assessed and follow-up MRI scan with same procedures as baseline will be collected. Total participation time for Visits 16-17 will be about 4 hours.

The assessment visit may be performed before, same-day, or after the MRI visit for ease of accommodating the schedule of the scanner or participant.

IN PERSON FOLLOW-UP: The participant will be asked to return 1- and 2-months after intervention to fill out the same clinical, cognitive and substance use questionnaires that were administered on Visits 2, 9, and 16. Follow-up visits will be about 1.5 hours each. Subjects will undergo saliva/urine tests evaluating recent drug/alcohol use.

At follow-up timepoints, we will contact subjects two weeks prior to the next follow-up to coordinate scheduling with sufficient time so that data is collected as close to the target as possible.

Retention: To maximize participant retention we will have all consented participants fill out a “contact” document in which they will provide at least two telephone numbers to be reached and one home address. We will ask participants to provide the phone number of a good friend or relative who will know their whereabouts to help us re-contacting the participant if needed. Before follow-up appointments, we will call participants over the phone to confirm their attendance and we will send reminder cards through regular mail. If participants give their consent, we will also send a text to their contact phone number.

5.3 Study Duration:

- The anticipated duration an individual participant’s participation in the study is 2.5-4 months since recruitment.

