15.0 Statistical Considerations

15.1 Data Analysis Plan: Compare brain FC between groups: Sham vs Active tDCS. Compare FC within groups to examine time effects: before and after intervention. Look for interaction effects (group x time).

15.2 Power Analysis: The study in reference is a pilot study for which a power analysis is not applicable.

15.3 Statistical Analysis: A mixed model analysis of variance will be conducted with between-group measures (sham vs active tDCS) and within-group measures (FC and craving reports before and after cognitive training and tDCS intervention). This mixed model analysis will examine main- and interaction-effects. To examine the long-term effects of cognitive training and tDCS, we will conduct a repeated measures analysis using longitudinal data collected at 1- and 2-month follow-up timepoints after intervention completion. A Log-rank (Mantel-Cox) Test (used in (Klauss et al. 2014) will be conducted to establish the efficacy of cognitive training and active tDCS vs. cognitive training and sham tDCS in the time domain.

15.4 Data Integrity: The principal investigator and co-investigator will monitor data quality for this study. They will ensure that data are generated, documented (recorded), and reported - in compliance with this protocol, with Good Clinical Practice, and any other applicable regulatory requirements.

PROTOCOL TITLE: Combining Neuro-Imaging and Non-Invasive Brain Stimulation for Clinical Intervention in Opioid Use Disorder

VERSION DATE: 2022-02-11

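### The long-term analysis in 15.3 names only the 1- and 2-month data, so it has no baseline adjustment and no end-of-intervention reference, although both are collected on the same measures

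*Combined protocol and SAP*

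**What the plan says.** Section 15.3 describes two separate models for repeated measures. The first is a mixed-model analysis of variance by arm, with "within-group measures (FC and craving reports before and after cognitive training and tDCS intervention" as the repeated part. Of this model the section says "This mixed model analysis will examine main- and interaction-effects". The second has a different purpose, "To examine the long-term effects of cognitive training and tDCS", and for it "we will conduct a repeated measures analysis using longitudinal data collected at 1- and 2-month follow-up timepoints after intervention completion". That sentence names no outcome, covariate, contrast or covariance structure. It does not mention the pre- or post-intervention values, either to include or to exclude them.

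Elsewhere the protocol collects those values for this kind of question. Section 5.1 says of the cognitive battery: "To examine generalization and durability effects of training, patients will be asked to complete the following tasks at pre-intervention, post-intervention, 1-month follow-up and 2-month follow-up". Section 3.2 gives the same four timepoints as a secondary endpoint. Section 5.2 has the follow-up visits repeat the "clinical, cognitive and substance use questionnaires that were administered on Visits 2, 9, and 16", that is, those of the pre-intervention, midpoint and post-intervention assessments. It lists no MRI at follow-up.

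Section 15.2 states that a power analysis does not apply to this pilot, so the plan has no sample size, effect size or correlation for the long-term analysis.

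**The concern.** Durability is a statement about follow-up relative to the end of the intervention. An analyst who follows 15.3 as written fits a model with two time levels, month 1 and month 2, and the end-of-intervention visit is not in it. If that model shows no arm difference, the trial cannot say from it whether the intervention worked and wore off or never worked. Those two results point to different next steps, such as booster sessions or a different target.

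The other model in 15.3 partly fills this gap for craving, since it estimates the change from before to after the intervention. It does not do so for cognition. Section 3.1 (Aim A3) promises a comparison of pre-to-post cognitive change between arms, but neither 15.1 nor 15.3 names a model for it.

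The second loss is precision. The pre-intervention score on the same test usually predicts the follow-up score. Leaving it out of the model puts between-person variation into the error term, and this trial is small.

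**Working it through.** The plan states no figure for this analysis, so there is none to reproduce. Two checks follow.

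**1. What a two-visit model can and cannot separate.** Take illustrative active-minus-sham differences, in SD, with 0.8 as an assumed effect. The two-visit arm effect is the mean of the month 1 and month 2 differences. Its arm-by-time term is month 2 minus month 1. The last column needs the post-intervention value.

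| Pattern | Post | Month 1 | Month 2 | Two-visit arm effect | Two-visit arm-by-time | Month 2 minus post |
|---|---|---|---|---|---|---|
| Lasting | 0.8 | 0.8 | 0.8 | 0.8 | 0 | 0 |
| Vanished by month 1 | 0.8 | 0 | 0 | 0 | 0 | -0.8 |
| Never present | 0 | 0 | 0 | 0 | 0 | 0 |

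The two-visit arm effect separates lasting (0.8) from vanished (0). No term in the two-visit model separates vanished from never present: both rows read 0 and 0. With the post-intervention value in the model, the arm difference at post and its change to month 2 identify all three patterns.

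**2. Precision of the follow-up arm difference.** Inputs, all assumed because the current text gives none:
- SD = 1 at each visit.
- Correlation r between months 1 and 2, and correlation b between baseline and each follow-up visit.
- 15 per arm. A goal of 30 completers appears only in the amendment log; allocation in 5.2 is 1:1.
- Two-sided alpha of 0.05.

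Formulas:
- Per-person variance of the mean of months 1 and 2, unadjusted: (1 + r)/2.
- After adjustment for baseline: (1 + r)/2 - b².
- Proportional reduction: b² / [(1 + r)/2].
- SE of the arm difference: √(2 × variance / 15).

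| b | r | Unadjusted variance | Adjusted variance | Reduction | SE unadjusted | SE adjusted |
|---|---|---|---|---|---|---|
| 0.3 | 0.3 | 0.65 | 0.56 | 14% | 0.294 | 0.273 |
| 0.5 | 0.5 | 0.75 | 0.50 | 33% | 0.316 | 0.258 |
| 0.7 | 0.7 | 0.85 | 0.36 | 58% | 0.337 | 0.219 |
| 0.8 | 0.8 | 0.90 | 0.26 | 71% | 0.346 | 0.186 |
| 0.4 | 0.7 | 0.85 | 0.69 | 19% | 0.337 | 0.303 |

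The first four rows assume compound symmetry (b = r). The last lets the baseline correlate less with follow-up than the two follow-up visits do with each other: 0.4² / 0.85 = 0.16 / 0.85 = 19%.

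The difference detectable with 80% power is (t₀.₉₇₅ + t₀.₈₀) × SE, with 28 df unadjusted and 27 df adjusted. At b = r = 0.5 it falls from (2.048 + 0.855) × 0.316 = 0.92 SD to (2.052 + 0.855) × 0.258 = 0.75 SD. At b = 0.4, r = 0.7 it falls from 2.903 × 0.337 = 0.98 SD to 2.907 × 0.303 = 0.88 SD. These figures ignore the small cost of estimating the covariate slope. Simulated power that includes it was within about one percentage point of the formula under compound symmetry.

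The change in the arm difference from post to month 2 has per-person variance 2(1 - r), and under compound symmetry baseline adjustment does not reduce it. At r = 0.5 its SE is √(2 × 1.0 / 15) = 0.365 SD. It should be reported as an estimate with an interval, not relied on as a test.

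**The case against.** The strongest defence is that 15.3 is brief rather than wrong. It does not say that earlier values are excluded, and the four-timepoint schedule in 3.2 and 5.1 makes it plausible that a comparison across all four was intended. That stands. A reader might infer that the plan discards the pre- and post-intervention data; the text supports only that it does not bring them into the long-term model. Since 15.3 names before-and-after data for one model and months 1 and 2 for the other, an analyst following it would still fit two time levels. The correction is the same on either reading.

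A reader might also infer that the analysis cannot tell a lasting effect from a vanished one, because the arm-by-time term is zero in both cases. The documents do not support this. Section 15.3 speaks of interaction effects only for the pre/post model and names no arm-by-time test at follow-up. Under randomisation the arm effect validly estimates the follow-up difference, and it does separate those two cases.

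Three further limits stand:
- Durability of cognition is a secondary aim. Section 5.1 gives querying substance use as the reason for the follow-up interviews, and for Aim A4 the follow-up arm difference is itself the endpoint. The two visits therefore do not exist solely to test persistence.
- The size of the gain rests on correlations that the documents do not give. Compound symmetry favours adjustment, since baseline may lie up to about four months before month 2. Normal-theory figures also do not carry over to substance use status or days of use.
- Baseline is not consistently documented for every test. The Visit One list in 5.2 has three D-KEFS tests and Digit-Span. It omits Digit Symbol (listed in 3.2) and the set-shift task (listed in 5.1).

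**Conclusion.** The point holds as a weakness in specification and efficiency. The follow-up arm comparison remains valid. Followed as written, the long-term model has no baseline covariate and no end-of-intervention reference, so on its own it cannot separate an effect that faded from one that never occurred. This matters most for cognition, where Section 15 names no model for the end-of-intervention difference. For craving the separate pre/post model supplies part of it. A reader might extend the point to FC, but no scan is listed at follow-up, so FC cannot enter a long-term model.

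The precision gain is real for any non-zero correlation of useful size, but its magnitude is illustrative: 14% to 71% of the variance for equal correlations of 0.3 to 0.8, and about 19% with 0.4 to baseline and 0.7 between follow-up visits. The proportional reductions do not depend on the 15 per arm; the standard errors and detectable differences do. Pilot status explains the absence of a power calculation, but it does not explain why the reference visits are missing from the model. The change should be made.

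**What to change.** Replace the long-term sentence in 15.3 with the following, for each continuous outcome measured at pre-intervention, post-intervention, 1 month and 2 months:
- Fit one longitudinal mixed model with the post-intervention, 1-month and 2-month values as outcomes, the pre-intervention value as covariate, and arm, visit and arm-by-visit as terms. State the covariance structure.
- Report the adjusted arm difference at each visit with its 95% CI.
- Define the durability contrast as the change in that difference from post-intervention to 2 months, also with a 95% CI, and read it beside the 2-month difference.
- List the outcomes covered: the cognitive tests with a documented baseline, and craving or clinical scores. Section 5.2 does not name craving in the follow-up list, so confirm that it is among the questionnaires repeated there. Exclude FC.
- Reconcile the test lists in 3.2, 5.1 and 5.2, so that it is clear whether Digit Symbol and the set-shift task have a baseline.

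Substance use status and days of use need their own stated method; this model is not meant for them.

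The cost is analysis wording and one model degree of freedom for the covariate. For the tests with a documented baseline, no visit or measurement is added.

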16.0 Confidentiality

16.1 Data Security: Trained research staff will be instructed to keep the content of the records confidential. During the initial consent process subjects will be told that they have the right to refuse to answer questions; however, this may affect whether they continue in the study. At all points in the study subjects will be warned at the beginning of procedures which involve the disclosure of personal and sensitive information. These warnings will occur in the introductory comments of interviews or in the instructions of questionnaires and surveys.

Only research staff will have access to subject information. Data contained on paper records and computer files will not include names or other identifying information of subjects. Records containing identifying information will be stored in a private research office in a locked file cabinet and be accessible only by the principal investigator and the study coordinator. The study coordinator or the principal investigator will review and remind research staff of this guideline on a regular basis. Paper and electronic records will be kept for 3 years or longer. Paper records not under use will be stored in locked file cabinets in a private research space. Any identifying information on magnetic or optical media will be stored in a similar manner or be password protected. The password for accessing this information will be available to only select staff that need access to the information to conduct their research duties. All other data will not contain identifying information. All other data will be stored on encrypted magnetic or optical media that is secured or on computer systems accessible only by research staff and computer system administrators via password.

No copy of the consent form or other research study information will be placed in the participants' medical, employment, or educational records.

17.0 Provisions to Monitor the Data to Ensure the Safety of Participants

17.1 Data Integrity Monitoring: The study will be monitored by CTSI in accordance with its institutionally approved monitoring plan.

17.2 Data Safety Monitoring: It is the responsibility of the Principal Investigator to oversee the safety of the study at his/her site. This safety monitoring will include careful assessment and appropriate reporting of adverse events. Medical monitoring will include a regular assessment of the number and type of serious adverse events.

18.0 Provisions to Protect the Privacy Interests of Participants

PROTOCOL TITLE: Combining Neuro-Imaging and Non-Invasive Brain Stimulation for Clinical Intervention in Opioid Use Disorder

VERSION DATE: 2022-02-11

18.1 Protecting Privacy: The study consent form will describe in detail any intrusive, uncomfortable, or unfamiliar questions, procedures, or interactions with researchers or study personnel that the participant will be asked to complete. Furthermore, the study consent form will communicate that it is the participant's right to opt-out of any study procedures or the study as a whole or withdraw from the study at any time and this information will be reiterated and revisited periodically throughout the study in advance of intrusive, uncomfortable, or unfamiliar questions procedures or interactions. Participants will not be compelled or pressured to provide information or specimens or study data that they do not wish to provide.

Access to Participants: Participants will be fully informed of the ways in which their data will/may be used during the informed consent process. The research team has been trained in conducting these conversations and the participants are also assessed for their understanding of consent prior to signing the consent form or initiating any study procedures.

19.0 Compensation for Research-Related Injury

19.1 Compensation for Research-Related Injury: There is no compensation in the event of research-related injury. The consent form states: "In the event that this research activity results in an injury, treatment will be available, including first aid, emergency treatment and follow-up care as needed. Care for such injuries will be billed in the ordinary manner, to you or the participant's insurance company. If you think that you have suffered a research-related injury, please let us know right away."

19.2 Contract Language: N/A

20.0 Consent Process

20.1 Consent Process (when consent will be obtained): Screening and consent will take place in a private room in Hennepin Healthcare.

The study research staff will thoroughly describe the study and read the consent form. Then the patient will be given time to read the consent form and ask questions of study staff. If the patient agrees, they will sign the consent with the study staff person looking on. Part of the consent involves asking questions of the patient and having him or her record their responses to ensure they understand the study and that they can terminate participation at any point. To protect vulnerable populations, if the patient does not seem to fully understand the nature of the study (including procedures, risks, confidentiality, voluntary nature), they will not be included in the study. They are also informed that study staff may terminate study participation at any point if they are concerned about the patient's welfare or behavior.

PROTOCOL TITLE: Combining Neuro-Imaging and Non-Invasive Brain Stimulation for Clinical Intervention in Opioid Use Disorder

VERSION DATE: 2022-02-11

The study staff person will thoroughly describe the study and read the consent form. Then the patient will be given time to read the consent form and ask questions of study staff. If the patient agrees they will sign the consent with the study staff person looking on. Part of the consent involves asking questions of the patient and having him or her record their responses to ensure they understand the study and that they can terminate participation at any point. To protect vulnerable populations, if the patient does not seem to fully understand the nature of the study (including procedures, risks, confidentiality, voluntary nature), they will not be included in the study. They are also informed that study staff may terminate study participation at any point if they are concerned about the patient's welfare or behavior.

To protect vulnerable populations, if the patient does not seem to fully understand the nature of the study (including procedures, risks, confidentiality, voluntary nature), they will not be included in the study. They are also informed that study staff may terminate study participation at any point if they are concerned about the patient's welfare or behavior.

To ensure ongoing consent: After consent is provided and at each intervention day, participants are monitored for any concerns they have about the intervention with the Treatment Side Effect Questionnaire. Participants who agree to continue in the study will sign this questionnaire daily.

20.2 Waiver or Alteration of Consent Process (when consent will not be obtained): N/A

